5.3.4 Assessment of Causality of Adverse Events

Investigators should use their knowledge of the study subject, the circumstances surrounding the event, and an evaluation of any potential alternative causes to determine whether or not an adverse event is considered to be related to the study drug, indicating "yes" or "no" accordingly. The following guidance should be taken into consideration:

- Temporal relationship of event onset to the initiation of study drug.
- Course of the event, considering especially the effects of dose reduction, discontinuation of study drug.
- Known association of the event with the study drug or with similar treatments.
- Known association of the event with the disease under study.
- Presence of risk factors in the study subject or use of concomitant medications known to increase the occurrence of the event.
- Presence of non-treatment-related factors that are known to be associated with the occurrence of the event.

For study subjects receiving combination therapy, causality will be assessed individually for each protocol mandated therapy.

5.3.5 Procedures for Recording Adverse Events

Investigators should use correct medical terminology/concepts when recording adverse events on the Adverse Event eCRF. Avoid colloquialisms and abbreviations.

Only one adverse event term should be recorded in the event field on the Adverse Event eCRF.

5.3.5.1 Diagnosis versus Signs and Symptoms

Injection-Site Reactions

Adverse events that occur during or after study drug administration and are judged to be local and related to the SC study drug injection should be captured as a diagnosis (e.g., "injection site reaction" on the Adverse Event eCRF. If possible, avoid ambiguous terms such as "systemic reaction.") Associated signs and symptoms should be recorded on the dedicated Injection Reaction eCRF.

Grading of pre-defined injection site reaction symptoms is described in [Appendix 17](#). If a patient experiences both a local and systemic reaction to the same dose of study drug, each reaction should be recorded separately on the Adverse Event eCRF, with signs and symptoms also recorded separately on the dedicated Injection Reaction eCRF.

Other Adverse Events

For adverse events, a diagnosis (if known) should be recorded on the Adverse Event eCRF rather than individual signs and symptoms (e.g., record only liver failure or hepatitis rather than jaundice, asterixis, and elevated transaminases). However, if a constellation of signs and/or symptoms cannot be medically characterized as a single diagnosis or syndrome at the time of reporting, each individual event should be recorded on the Adverse Event eCRF. If a diagnosis is subsequently established, all previously reported adverse events based on signs and symptoms should be nullified and replaced by one adverse event report based on the single diagnosis, with a starting date that corresponds to the starting date of the first symptom of the eventual diagnosis.

5.3.5.2 Adverse Events Occurring Secondary to Other Events

In general, adverse events occurring secondary to other events (e.g., cascade events or clinical sequelae) should be identified by their primary cause, with the exception of severe or serious secondary events. However, medically significant adverse events occurring secondary to an initiating event that are separated in time should be recorded as independent events on the Adverse Event eCRF. For example:

- If vomiting results in mild dehydration with no additional treatment in a healthy adult, only vomiting should be reported on the eCRF.
- If vomiting results in severe dehydration, both events should be reported separately on the eCRF.
- If a severe gastrointestinal hemorrhage leads to renal failure, both events should be reported separately on the eCRF.
- If dizziness leads to a fall and subsequent fracture, all three events should be reported separately on the eCRF.

All adverse events should be recorded separately on the Adverse Event eCRF if it is unclear as to whether the events are associated.

5.3.5.3 Persistent or Recurrent Adverse Events

A persistent adverse event is one that extends continuously, without resolution, between healthy volunteer/patient evaluation time-points. Such events should only be recorded once on the Adverse Event eCRF. The initial severity of the event should be recorded, and the severity should be updated to reflect the most extreme severity any time the event worsens. If the event becomes serious, the Adverse Event eCRF should be updated to reflect this.

A recurrent adverse event is one that resolves between patient evaluation time-points and subsequently recurs. Each recurrence of an adverse event should be recorded separately on the Adverse Event eCRF.

5.3.5.4 Abnormal Laboratory Values

Not every laboratory abnormality qualifies as an adverse event. A laboratory test result should be reported as an adverse event if it meets any of the following criteria:

- Accompanied by clinical symptoms
- Results in a change in study treatment (e.g., dosage modification, treatment interruption, or treatment discontinuation)
- Results in a medical intervention (e.g., potassium supplementation for hypokalemia) or a change in concomitant therapy
- Clinically significant in the Investigator's judgment

It is the Investigator's responsibility to review all laboratory findings. Medical and scientific judgment should be exercised in deciding whether an isolated laboratory abnormality should be classified as an adverse event.

If a clinically significant laboratory abnormality is a sign of a disease or syndrome (e.g., alkaline phosphatase and bilirubin 5 times the upper limit of normal (ULN) associated with cholecystitis), only the diagnosis (i.e., cholecystitis) should be recorded on the Adverse Event eCRF.

If a clinically significant laboratory abnormality is not a sign of a disease or syndrome, the abnormality itself should be recorded on the Adverse Event eCRF, along with a descriptor indicating if the test result is above or below the normal range (e.g., "elevated potassium", as opposed to "abnormal potassium"). If the laboratory abnormality can be characterized by a precise clinical term per standard definitions, the clinical term should be recorded as the adverse event. For example, an elevated serum potassium level of 7.0 mEq/L should be recorded as "hyperkalemia".

Observations of the same clinically significant laboratory abnormality from visit to visit should not be repeatedly recorded on the Adverse Event eCRF, unless the etiology changes. The initial severity of the event should be recorded, and the severity or seriousness should be updated any time the event worsens.

5.3.5.5 Abnormal Vital Sign Value

Not every vital sign abnormality qualifies as an adverse event. A vital sign result should be reported as an adverse event if it meets any of the following criteria:

- Accompanied by clinical symptoms
- Results in a change in study treatment (e.g., dosage modification, treatment interruption, or treatment discontinuation)
- Results in a medical intervention or a change in concomitant therapy
- Clinically significant in the Investigator's judgment

It is the Investigator's responsibility to review all vital sign findings. Medical and scientific judgment should be exercised in deciding whether an isolated vital sign abnormality should be classified as an adverse event.

If a clinically significant vital sign abnormality is a sign of a disease or syndrome (e.g., high blood pressure), only the diagnosis (i.e., hypertension) should be recorded on the Adverse Event eCRF.

Observations of the same clinically significant vital sign abnormality from visit to visit should not be repeatedly recorded on the Adverse Event eCRF, unless the etiology changes. The initial severity of the event should be recorded, and the severity or seriousness should be updated any time the event worsens.

5.3.5.6 Alanine and Aspartate Transaminases (ALT/AST) Elevations For Part 1:

The finding of an elevated ALT or AST ($>3 \times \text{ULN}$) in combination with either an elevated total bilirubin ($>2 \times \text{ULN}$) or clinical jaundice in the absence of cholestasis or other causes of hyperbilirubinemia is considered to be an indicator of severe liver injury (*Hy's Law*). Therefore, investigators must report as an adverse event the occurrence of either of the following:

- Treatment-emergent ALT or AST $>3 \times \text{ULN}$ in combination with total bilirubin $>2 \times \text{ULN}$.
- Treatment-emergent ALT or AST $>3 \times \text{ULN}$ in combination with clinical jaundice.

For Part 2:

CHB patients may have elevated baseline ALT levels without an increase in bilirubin. However, the finding of an elevated ALT in combination with either an elevated total bilirubin or clinical jaundice in the absence of cholestasis or other causes of hyperbilirubinemia is considered to be an indicator of potential severe liver injury or worsening of disease. Therefore, investigators must report as an adverse event the occurrence of either of the following:

- Treatment-emergent ALT $> 3 \times$ Baseline and $> 3x$ ULN value in combination with total bilirubin $> 2 \times$ ULN.
- Treatment-emergent ALT $> 3 \times$ Baseline and $> 3x$ ULN value in combination with clinical jaundice.

**For Part 2c (treatment-naïve and immune-active CHB patients), the threshold of ALT $> 3 \times$ ULN baseline will be capped at $10 \times$ ULN.*

The most appropriate diagnosis or (if a diagnosis cannot be established) the abnormal laboratory values should be recorded on the Adverse Event eCRF (see Section 5.3.5.1) and reported to the Sponsor immediately (i.e., no more than 24 hours after learning of the event), either as a serious adverse event or a non-serious adverse event of special interest (see Section 5.4.2).

5.3.5.7 Deaths

All deaths that occur during the protocol-specified adverse event reporting period (see Section 5.3.1), regardless of relationship to study drug, must be recorded on the Adverse Event eCRF and immediately reported to the Sponsor (see Section 5.4.2). This includes death attributed to progression of chronic hepatitis B.

Death should be considered an outcome and not a distinct event. The event or condition that caused or contributed to the fatal outcome should be recorded as the single medical concept on the Adverse Event eCRF. Generally, only one such event should be reported. The term “sudden death” should only be used for the occurrence of an abrupt and unexpected death due to presumed cardiac causes in a patient with or without preexisting heart disease, within 1 hour of the onset of acute symptoms or, in the case of an unwitnessed death, within 24 hours after the patient was last seen alive and stable. If the cause of death is unknown and cannot be ascertained at the time of reporting, “unexplained death” should be recorded on the Adverse Event eCRF. If the cause of death later becomes available (e.g., after autopsy), “unexplained death” should be replaced by the established cause of death.

5.3.5.8 Pre-Existing Medical Conditions

A pre-existing medical condition is one that is present at the Screening visit for this study. Such conditions should be recorded on the General Medical History and Baseline Conditions eCRF.

A pre-existing medical condition should be recorded as an adverse event only if the frequency, severity, or character of the condition worsens during the study. When recording such events on the Adverse Event eCRF, it is important to convey the concept that the preexisting condition has changed by including applicable descriptors (e.g., “more frequent headaches”).

5.3.5.9 Lack of Efficacy or Worsening of Chronic Hepatitis B Infection

As this is the first study of RO7062931 in humans as well as in CHB patients and these patients are virologically suppressed, the effect on HBsAg is being explored as part of the secondary endpoints in this study. The short duration of treatment RO7062931 is not anticipated to provide the patients with therapeutic benefit, but rather to give evidence on the effect of multiple doses of RO7062931 on HBsAg.

Therefore, lack of RO7062931 efficacy in terms of changes in HBsAg does not qualify for adverse event in Part 2 of this study.

Medical occurrences or symptoms of deterioration in a course of chronic HBV infection should be recorded as adverse events if judged by the Investigator to have unexpectedly worsened in severity or frequency or changed in nature at any time during the study.

Virological breakthrough (Section 4.6.1.5.3), and abnormal liver function tests (as defined in Section 5.3.5.6) should be reported as adverse events. Hepatic flares should be reported as adverse events of special interest (Section 5.1.3).

5.3.5.10 Hospitalization or Prolonged Hospitalization

Any adverse event that results in hospitalization or prolonged hospitalization should be documented and reported as a serious adverse event (per the definition of serious adverse event in Section 5.1.2), except as outlined below.

The following hospitalization scenarios are not considered to be serious adverse events:

- Hospitalization for respite care
 - Planned hospitalization required by the protocol.
- Hospitalization for a preexisting condition, provided that all of the following criteria are met:
 - The hospitalization was planned prior to the study or was scheduled during the study when elective surgery became necessary because of the expected normal progression of the disease.
 - The study subject has not suffered an adverse event.

The following hospitalization scenarios are not considered to be serious adverse events, but should be reported as adverse events instead:

- Hospitalization for an adverse event that would ordinarily have been treated in an outpatient setting had an outpatient clinic been available.

5.3.5.11 Overdoses

Study drug (*including IMP and NIMP*) overdose is the accidental or intentional use of the drug in an amount higher than the dose being studied. An overdose or incorrect administration of study drug is not an adverse event unless it results in untoward medical effects.

Any study drug overdose or incorrect administration of study drug should be noted on the Study Drug Administration eCRF.

All adverse events associated with an overdose or incorrect administration of study drug should be recorded on the Adverse Event eCRF. If the associated adverse event fulfills serious criteria, the event should be reported to the Sponsor immediately (i.e., no more than 24 hours after learning of the event; see Section 5.4.2).

5.4 IMMEDIATE REPORTING REQUIREMENTS FROM INVESTIGATOR TO SPONSOR

Certain events require immediate reporting to allow the Sponsor to take appropriate measures to address potential new risks in a clinical trial. The Investigator must report such events to the Sponsor immediately; under no circumstances should reporting take place more than 24 hours after the Investigator learns of the event. The following is a list of events that the Investigator must report to the Sponsor within 24 hours after learning of the event, regardless of relationship to study drug:

- Serious adverse events
- Non-serious adverse events of special interest
- Pregnancies

The Investigator must report new significant follow-up information for these events to the Sponsor immediately (i.e., no more than 24 hours after becoming aware of the information). New significant information includes the following:

- New signs or symptoms or a change in the diagnosis
- Significant new diagnostic test results
- Change in causality based on new information
- Change in the event's outcome, including recovery
- Additional narrative information on the clinical course of the event

Investigators must also comply with local requirements for reporting serious adverse events to the local health authority and IRB/EC.

5.4.1 Emergency Medical Contacts

To ensure the safety of study patients, access to the Medical monitors is available 24 hours a day 7 days a week. Medical monitors' contact details will be available on a separate list generated by the study management team.

5.4.2 Reporting Requirements for Serious Adverse Events and Non-Serious Adverse Events of Special Interest

After informed consent has been obtained but prior to initiation of study drug, only serious adverse events caused by a protocol-mandated intervention should be reported. The Serious Adverse Event / Adverse Event of Special Interest Reporting Form provided to investigators should be completed and submitted to the SAE responsible immediately (i.e., no more than 24 hours after learning of the event).

For reports of serious adverse events and non-serious adverse events of special interest (see Sections [5.1.2](#) and [5.1.3](#)) that occur after initiation of study drug, investigators should record all case details that can be gathered on the Serious Adverse Reporting Form and forward this form to the SAE Responsible within 24 hours.

In the case of electronic reporting, investigators should record all case details that can be gathered immediately (i.e., within 24 hours after learning of the event) on the appropriate Serious Adverse Event / Adverse Event of Special Interest eCRF form and submit the report via the electronic data capture (EDC) system. A report will be generated and sent to the Sponsor's Safety Risk Management department.

In the event that the EDC system is unavailable, the Serious Adverse Event / Adverse Event of Special Interest Reporting Form provided to investigators should be completed and submitted to the SAE Responsible immediately (i.e., no more than 24 hours after learning of the event).

Once the EDC system is available, all information will need to be entered and submitted via the EDC system.

5.4.3 Reporting Requirements for Pregnancies

5.4.3.1 Pregnancies in Female Patients

Female subjects of childbearing potential will not be allowed to participate in this study. Although highly unlikely, female subjects will be instructed to immediately inform the Investigator if they become pregnant during the study or within 105 days after the last dose of study drug (*Parts 2a and 2b*) or within 6 months after last dose (*Part 2c*). A Clinical Trial Pregnancy Reporting Form should be completed by the Investigator and submitted to the sponsor within 24 hours after learning of the pregnancy. Pregnancy should not be recorded on the Adverse Event eCRF. The Investigator should discontinue study drug and counsel the patient, discussing the risks of the pregnancy and the possible effects on the fetus. Monitoring of the patient should continue until conclusion of the pregnancy.

5.4.3.2 Pregnancies in Female Partners of Male Study Subjects

Male patients will be instructed through the Informed Consent Form to immediately inform the Investigator if their partner becomes pregnant during the study or within 105 days after the last dose of study drug. A Clinical Trial Pregnancy Reporting Form should be completed by the Investigator and submitted to the Sponsor within 24 hours after learning of the pregnancy. Attempts should be made to collect and report details of the course and outcome of any pregnancy in the partner of a male study subject exposed to study drug. The pregnant partner will need to sign an Authorization for Use and Disclosure of Pregnancy Health Information to allow for follow-up on her pregnancy. Once the authorization has been signed, the Investigator will update the Clinical Trial Pregnancy Reporting Form with additional information on the course and outcome of the pregnancy. An Investigator who is contacted by the male study subject or his pregnant partner may provide information on the risks of the pregnancy and the possible effects on the fetus, to support an informed decision in cooperation with the treating physician and/or obstetrician.

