All doses in Part 2 will be lower than, or equal to, the doses studied and considered to be well-tolerated in Part 1. Subsequent doses and regimens for Part 2b/2c will be selected on the basis of the analysis of Part 2a data. Part 2b will be initiated once Part 2a data have been analyzed. *The* total dose will not exceed 400 mg per day.

Due to the adaptive nature of this study, the actual number of dose levels and the number of study subjects/cohorts at each dose may be modified depending on emerging data. Planned doses may be adjusted (increased, decreased, or repeated) or dosing may be discontinued. After safety and PK data review (see Section [3.1.4](#)), study subjects may be requested to return to the site for additional safety or PK assessments, upon agreement between subjects, Investigators and the Sponsor.

3.1.1.3 *Part 2c: Extended Duration of RO7062931 Therapy in CHB Infected Patients*

Part 2c is an adaptive, open-label, non-controlled, multi-arm, multi-center, study to evaluate the efficacy and safety of RO7062931 following subcutaneous administration on top of SoC therapies (a NUC with/without PEG-IFN) in NUC-suppressed or treatment-naïve CHB patients ([Figure 2](#)). Both HBeAg positive and negative patients will be enrolled.

- *Cohort 9 will enroll NUC-suppressed CHB patients. Patients will receive RO7062931 on top of a NUC for up to 24 weeks. RO7062931 will be administered at a dose determined from study Parts 2a and 2b.*
- *Cohort 10 will enroll NUC-suppressed CHB patients. Patients will receive RO7062931 on top of a NUC plus PEG-IFN for up to 48 weeks. RO7062931 will be administered at a dose determined from study Parts 2a and 2b.*
- *Cohort 11 and 12 (optional cohorts) may enroll treatment-naïve immune-active CHB patients and/or different treatment combinations or treatment duration.*

All cohorts will initially enroll approximately 8 CHB patients per cohort. Initially the enrollment will occur sequentially (Cohort 9 will be followed by Cohort 10, see Section 4.3). At the end of treatment (either 24 or 48 weeks depending on cohort), all study treatment (RO7062931 and PEG-IFN) will be discontinued and all patients will be followed up for at least 24 weeks post-treatment follow up.

Based on emerging and accumulated PK, PD, efficacy and safety data from this study or other related studies, the initial cohorts may be expanded to enroll a total of 30 CHB patients. Enrollment of the expanded cohorts may be either sequential or parallel.

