5. Positive test for HBsAg for more than 6 months prior to randomization.
6. HBsAg titer $\geq 10^3$ IU/mL at screening.
7. On entecavir, tenofovir, adefovir or telbivudine treatment for at least 6 months prior to randomization and will remain on stable treatment during the study.
8. HBV DNA ≤ 90 IU/mL for at least the preceding 6 months.
9. Screening laboratory values (hematology, chemistry, urinalysis) obtained up to 56 days prior to first study treatment within normal ranges, with the exception of otherwise specified criteria or judged to be not clinically significant by Principal Investigator (PI) and Medical Monitor.
10. Alanine transaminase (ALT), aspartate aminotransferase (AST), γ -glutamyltransferase (GGT), and alkaline phosphatase (ALP) at screening $\leq 1.5 \times$ upper limit of normal (ULN); normal values for total bilirubin and prothrombin time (PT)/International Normalized Ratio (INR)/activated partial thromboplastin time (aPTT) tests at screening (except for patients with Gilbert's syndrome TB ≤ 47 μ mol/L [2.75 mg/dL]).

11. Liver biopsy, Fibroscan® or equivalent test obtained within the past 6 months demonstrating liver disease consistent with chronic HBV infection without evidence of bridging fibrosis or cirrhosis (\geq Metavir 3, recommended cut-off for fibroscan 8.5 kPa).
12. Women should be of non-childbearing potential. A woman is considered to be of childbearing potential if she is post-menarcheal but has not reached a post-menopausal state (\geq 12 continuous months of amenorrhea with no identified cause other than menopause, confirmed by follicle-stimulating hormone [FSH], or amenorrhea for at least 24 months if on hormone replacement therapy), and has not undergone surgical sterilization (removal of ovaries and/or uterus).

All males must agree to remain abstinent (refrain from heterosexual intercourse) or use contraceptive measures, and agreement to refrain from donating sperm, as defined below:

With female partners of childbearing potential or pregnant female partners, men must remain abstinent or use a condom during the treatment period and up to 105 days after the last dose to avoid exposing the embryo. Men must refrain from donating sperm during this same period.

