 9. *Women should be of non-childbearing potential. A woman is considered to be of childbearing potential if she is post-menarcheal but has not reached a post-menopausal state (\geq 12 continuous months of amenorrhea with no identified cause other than menopause, confirmed by FSH, or amenorrhea for at least 24 months if on hormone replacement therapy), and has not undergone surgical sterilization (removal of ovaries and/or uterus).*

All males must agree to remain abstinent (refrain from heterosexual intercourse) or use contraceptive measures, and agreement to refrain from donating sperm, as defined below:

With female partners of childbearing potential or pregnant female partners, men must remain abstinent or use a condom plus spermicide during the treatment period and up to 6 months after the last dose to avoid exposing the embryo. Men must refrain from donating sperm during this same period.

The reliability of sexual abstinence should be evaluated in relation to the duration of the clinical trial and the preferred and usual lifestyle of the patient. Periodic abstinence (e.g., calendar, ovulation, symptothermal, or post-ovulation methods) and withdrawal are not acceptable methods of contraception.

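### In Part 2c, the 105-day partner-pregnancy notification window in Section 5.4.3.2 disagrees with the 6-month windows in Sections 4.2.2.3 and 5.4.3.1

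*Combined protocol and SAP*

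**What the plan says.** Three places in the current protocol set a post-dose period connected with pregnancy.

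- **Partner pregnancy (Section 5.4.3.2).** Male patients are instructed through the consent form to tell the investigator of a partner pregnancy that arises while they are in the study or "within 105 days after the last dose of study drug". No study part is named, so the sentence applies to all of them.
- **Pregnancy in female patients (Section 5.4.3.1).** The period is split by part: 105 days for Parts 2a and 2b, and "within 6 months after last dose" for Part 2c.
- **Male contraception (Section 4.2.2).** In Parts 1, 2a and 2b the requirement on male subjects is to "remain abstinent or use a condom during the treatment period and up to 105 days after the last dose to avoid exposing the embryo". In Part 2c (Section 4.2.2.3, criterion 9) the measure applies "during the treatment period and up to 6 months after the last dose to avoid exposing the embryo", and sperm donation is barred for the same period. The synopsis repeats this.

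The length of follow-up also matters, because the first limb of the partner instruction covers the man while he is in the study. For Part 2c, Section 3.1.1.3 says that "all patients will be followed up for at least 24 weeks post-treatment follow up". Section 3.1.1 and the synopsis give 24 weeks as an upper limit instead.

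**The concern.** For Part 2c the protocol treats a man's partner as at risk of an exposed pregnancy for 6 months after his last dose, but tells him to notify a pregnancy for a shorter period. The mismatch affects Part 2c alone, the part with the longest exposure (weekly dosing for up to 48 weeks).

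Partner pregnancy is also the more plausible of the two routes. Women of childbearing potential are excluded, and Section 5.4.3.1 itself regards pregnancy in a female subject as improbable. Men with partners of childbearing potential may enrol. The Part 2c period was thus added to notification by women and not to notification by men.

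What is at stake is ascertainment. Spontaneous abortion (Section 5.4.3.3) and congenital anomaly in a partner's child (Section 5.4.3.4) are serious adverse events, and capturing them usually begins with someone telling the site about the pregnancy. For a partner, that is largely the man himself.

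**Working it through.** No sample size, power or error rate is involved. The check compares the windows side by side and then does day arithmetic.

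**Step 1. Post-dose windows by part**

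| | Part 1 | Parts 2a, 2b | Part 2c |
|---|---|---|---|
| Male contraception (4.2.2.1 to 4.2.2.3) | 105 days | 105 days | 6 months |
| Female-patient notification (5.4.3.1) | none labelled | 105 days | 6 months |
| Partner notification (5.4.3.2) | in study, or 105 days | in study, or 105 days | in study, or 105 days |

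For Parts 1, 2a and 2b, male contraception minus the stated partner window is 105 − 105 = 0 days. Only the Part 2c column disagrees.

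**Step 2. Inputs for Part 2c**

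- W, the 6-month window: 181 to 184 days, depending on the calendar months (assumption).
- Stated partner window: 105 days (5.4.3.2).
- d, the day after last dose on which the man's participation ends. For completers this is 24 weeks = 24 × 7 = 168 days. Appendices 11 and 13 place the last visits at Weeks 48 and 72, which are 24 weeks after Weeks 24 and 48, each with a window of ±7 days.

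**Step 3. Formula**

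The instruction covers the man to the later of day 105 and day d, so:

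uncovered days = W − max(105, d)

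**Step 4. Results**

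- Completes follow-up, d = 168: 181 − 168 = 13 to 184 − 168 = 16 days.
- Last visit a week late, shorter W: d = 168 + 7 = 175, and 181 − 175 = 6 days.
- Last visit a week early, longer W: d = 168 − 7 = 161, and 184 − 161 = 23 days.
- Leaves the study on or before day 105: 181 − 105 = 76 to 184 − 105 = 79 days. As a share of the window this is 76/181 = 42% to 79/184 = 43%.
- Leaves between days 105 and 168: a value between the completer and early-leaver results.

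**Step 5. Who is an early leaver**

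Stopping treatment early is not leaving the study. Section 4.7.1.1 keeps such patients in a 4-week follow-up and then in safety follow-up under the schedule of assessments, so the first limb of the instruction still covers them. The 76 to 79 days apply only to men who leave the study itself.

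The documents give no expected number of such men and no share of men with partners of childbearing potential. The gap therefore cannot be turned into an expected count of pregnancies. Initial cohorts are about 8 patients each.

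**The case against.** The strongest reply is that the 105 days limits only the patient's instruction. Section 5.4 requires investigators to report pregnancies within 24 hours of learning of them. Section 5.4.3.2 asks for attempts to obtain the course and outcome of a pregnancy in the partner of any exposed man, and Section 5.4.3.4 makes a congenital anomaly in a partner's child a serious adverse event. None of these carries a day limit. This stands. A reader might infer that exposed pregnancies between day 105 and 6 months need not be reported; the documents do not support that. What survives is narrower: those duties start only when the investigator learns of the pregnancy, which for a partner depends largely on the man saying so.

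A second reply is that participation in follow-up covers most of the window, so an 11-week gap does not apply to Part 2c men in general. This also stands, and it brings the usual gap down to about two weeks.

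Third, for men who withdraw consent, Section 4.7.1.2 rules out further follow-up, so a longer notification period would recover little from them. That is fair for withdrawals of consent. It is less so for men who leave for other reasons and could still act on what the consent form told them.

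Fourth, no endpoint is touched. Pregnancy is an immediately reportable event, but it is not among the safety outcome measures in Section 3.3.1, so it would be wrong to say that a study outcome is compromised.

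**Conclusion.** The inconsistency is real, lies in the current text and is confined to Part 2c. Men in Part 2c are not told to notify partner pregnancies in the last stretch of the protocol's own 6-month window: about 13 to 16 days for completers (6 to 23 days with the visit window), and up to 76 to 79 days for men who leave the study by day 105. It reads as a missed conforming edit. The other parts agree, the Version 4 summary of changes shows the Part 2c period entering Section 5.4.3.1 with no entry for 5.4.3.2, and nothing in the documents explains a shorter period for partners.

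The figures rest on 6 months being 181 to 184 days, on follow-up of 24 weeks, and on reading the first limb as the man's own participation. If it meant the whole study, whose end Section 3.1.5 ties to the last patient's last visit, earlier enrolees would be covered for longer. The protocol does not say which is meant.

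Two further inferences should be resisted. The consent form is not available here, so it cannot be called wrong; it carries the 105 days only if it follows Section 5.4.3.2. And the documents show that the windows disagree, not which of them is right. The consequence is a small loss in safety ascertainment, with no effect on any analysis.

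**What to change.** Reconcile Section 5.4.3.2 with Sections 4.2.2.3 and 5.4.3.1. State the partner-notification window by part, as 5.4.3.1 does for female patients, so that the Part 2c periods agree, or keep a difference and give the reason for it. In the same sentence, say whether the in-study limb means the man's own participation, and settle whether Part 2c follow-up is a minimum or a maximum of 24 weeks. If the consent form follows 5.4.3.2, change its matching line.

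The cost is one sentence in the protocol and one line in the consent form. It adds no visits or assessments and does not affect the sample size or the analysis.
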